10.5. Physical examination

A full physical examination will be performed at Screening. It will focus on clinical signs and symptoms which strongly suggest the presence of cirrhosis, such as palmar erythema, spider nevi, dilated abdominal wall veins, ascites, asterixis, gynecomastia, and loss of body or pubic hair.

A symptom targeted physical examination will be performed at day 1 and at all subsequent visits. It should include vital signs (oral temperature, pulse, and respiratory rate, and resting blood pressure)

and is to be driven by any previously identified or new signs or symptoms including diagnoses that the subject has experienced since the last visit.

10.6. ECG

Patients taking beta blockers or those with underlying cardiac comorbidities and/or advanced liver disease may be at increased risk for symptomatic bradycardia.

A 12 leads ECG will be performed at Screening and at week 1. It will also be performed at any time there is symptom suggestive of a cardiac event or signs of irregular heart beat or bradycardia. Patients will be referred to a cardiologist in case of unclear anomaly. Also, patients will be instructed to consult immediately in case of malaise, dizziness, light headedness, fainting spell, bradycardia or irregular heartbeat. An ECG will be repeated at the end of the treatment (resp. week 12 or week 24) and at SVR4 visit on patients showing ECG abnormalities at end of treatment visit.

Descriptive statistics for change from baseline to the end-of-study visit will be provided for each ECG parameter. ECG results will be reviewed for clinically notable abnormalities ("clinically significant"). Subjects exhibiting clinically notable ECG abnormalities (after re-test) will be listed. AEs will be recorded for clinically notable abnormalities that are considered clinically significant in the judgment of the Investigator.

QTcF value at baseline is < 450 milliseconds. A QTcF value increase up to 500 milliseconds during study conduct is accepted.

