¹³ A series of long-term follow-up visits will be implemented retrospectively for stage 1 for all patients with virological failure at SVR 12 or SVR 24 and for stage 2 for a representative subset of the cured patients (i.e. achieving SVR 12) and for all patients with virological failure at SVR 12 or SVR 24 and for stage 2 for a representative subset of the cured patients (i.e. achieving SVR 12) and for all patients with virological failure at SVR 12 or SVR 24 and for stage 2 for a representative subset of the cured patients (i.e. achieving SVR 12) and for all patients with virological failure at SVR 12 or SVR 24 (see section 13.5.2).

¹⁴ ECG at SVR4 visit will be performed only on patients showing ECG abnormalities at end of treatment visit.

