10.3. HCV testing

A quantitative HCV RNA viral load is essential to confirm that subjects with a positive HCV antibody test have chronic HCV infection, and establish pre-treatment baseline viral load levels. Blood sample for HCV RNA PCR testing will be collected, processed, and shipped to the designated laboratory. Results will be reported within 2 weeks after specimen receipt. Additional plasma will be stored to allow confirmatory tests: genotyping, viral load, presence of prescribed or non-prescribed drugs.

HCV chronic infection confirmation and initial evaluations

HCV RNA positive patients will be further explained the study process including baseline evaluations, the need for referral to the academic/dedicated site for liver fibrosis staging or on-site appointment for fibrosis staging depending on availability of the Fibroscan equipment and/or the results of APRI score, nature and duration of treatment dependent on the presence/absence liver cirrhosis and potential side-effects. They will also be explained all study clinical and biological procedures up through the end of the study visit (i.e. post-treatment follow-up Week 24 or end of long term follow-up for subset of cured patients or patients with virological failure).

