13.5. Follow-up visits

13.5.1. SVR4, SVR 12, SVR 24 and end of study visit

The week 4 post-treatment visit will have a window of -1 day and +7 days

The week 12 post-treatment visit (SVR 12, key endpoint) will have a window of -1 day and +28 days.

The week 24 post-treatment visit (SVR 24) will have a window of -3 days and +28 days.

This final visit will focus on assessing SVR 24 weeks after treatment discontinuation. Post-treatment study follow-up is of critical importance and is essential to preserving subject safety and the integrity of the study. Subjects who discontinue study treatment must continue to be followed for collection of outcome and/or survival follow-up data.

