13.5.2. Long term follow-up visits

A series of long-term follow-up visits will be implemented retrospectively for stage 1 (only for newly consented patients with virological failure) and for stage 2.

A representative subset of the cured patients (i.e achieving SVR12) will be followed up for one year after end of treatment to assess durability of response. One additional follow-up visit will be scheduled 12 months (+/- 28 days) after the end of treatment visit

All patients with virological failure at SVR12 or SVR24 will be followed up for three years after end of treatment or until they receive another treatment for HCV, whichever comes first. Five additional follow-up visits will be scheduled at one year, 18 months, 2 years, 30 months and 3 years after the end of treatment visit. Each of these long term follow-up visits has a window of +/- 28 days.

The following assessments will be performed at each long term follow-up visit, depending on cirrhosis status and achievement of SVR12 and SVR24:

	Non-Cirrhotics	Cirrhotics
Cured patients	HCV viral load and genotyping	HCV viral load and genotyping
-	Biochemistry and Haematology blood	Biochemistry and Haematology blood
(1 year FU post	sample ¹	sample ¹
end of treatment)	Symptom directed assessment	Symptom directed assessment
ŕ	AE review ²	AE review ²
Stage 2 only		INR ³
		Fibroscan ⁴
		Ultrasound⁵
Patients with virological failures (3 years FU post end of treatment)	HCV viral load and genotyping and resistance assessment Biochemistry and Haematology blood sample ¹	HCV viral load and genotyping and resistance assessment Biochemistry and Haematology blood sample ¹
Stage 1 and stage 2	Symptom directed assessment AE review ² INR ³ Fibroscan ⁴	Symptom directed assessment AE review ² INR ³ Fibroscan ⁴ Ultrasound ⁵

¹ Biochemistry and haematology including ALT and AST and bilirubine (direct and free)

²AE monitoring as per safety section

³ INR is performed to assess the evolution of the liver condition

⁴A Fibroscan is performed to assess the evolution of fibrosis

⁵ An ultrasound is performed to assess the occurrence of HCC as part as the standard of care.

14. Samples management

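### Section 10.6 summarises ECG change at the end-of-study visit, but no ECG is scheduled there; the ECGs taken in every subject are at week 1 and end of treatment

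*Protocol*

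**What the plan says.** Section 10.6 gives both the ECG timing and the ECG analysis. On timing, "A 12 leads ECG will be performed at Screening and at week 1", and later "An ECG will be repeated at the end of the treatment (resp. week 12 or week 24) and at SVR4 visit", the SVR4 recording being limited to subjects whose end-of-treatment ECG was abnormal. Further ECGs are taken only when symptoms or signs call for them. On analysis, "Descriptive statistics for change from baseline to the end-of-study visit will be provided for each ECG parameter". Section 16.2.5 (Safety Analysis) adds no other ECG change statistic.

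The visit named in that sentence is described in two places. Section 10.3 speaks of the "end of the study visit (i.e. post-treatment follow-up Week 24 or end of long term follow-up" for certain groups. Section 13.5.1, on the post-treatment week 24 visit, says "This final visit will focus on assessing SVR 24 weeks after treatment discontinuation".

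Footnote 14 of schedule 7.1 confirms the condition on the last ECG: "ECG at SVR4 visit will be performed only on patients showing ECG abnormalities at end of treatment visit". Footnote 15 of schedule 7.2 says the same for cirrhotic subjects.

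**The concern.** The analysis sentence names a single visit, and it is one at which the protocol collects no routine ECG. An analyst who follows it literally has nothing to tabulate except a chance symptom-triggered recording. The recordings that can show an effect of treatment on QTcF or heart rate, at week 1 and end of treatment, are left out.

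Cardiac safety is an explicit concern in this protocol. Subjects with QTcF of 450 ms or more at baseline are excluded (5.3). Methadone and efavirenz are allowed within that limit (5.3, 9.3). A QTcF of up to 500 ms is accepted during the study, and 10.6 warns of symptomatic bradycardia. The one ECG summary in the protocol should therefore point at the on-treatment data.

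**Working it through.** There is no planned figure to reproduce. The check sets the sentence in 10.6 against every place where an ECG is scheduled.

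**Step 1. Where ECGs are scheduled.**

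| Visit | 7.1, non-cirrhotic | 7.2, cirrhotic |
|---|---|---|
| Screening | yes | yes |
| Day 1 | no | no |
| Week 1 | yes | yes |
| End of treatment | yes (week 12) | yes (week 24) |
| Follow-up week 4 (SVR4) | only if end-of-treatment ECG abnormal | only if end-of-treatment ECG abnormal |
| Follow-up week 12 | no | no |
| Follow-up week 24 | no | no |
| Long-term follow-up | no | no |

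The timing text in 10.6 agrees with both schedules, so the blanks are not an accident of table layout.

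**Step 2. The long-term follow-up table.** In 13.5.2, "The following assessments will be performed at each long term follow-up visit", set out in 2 outcome rows × 2 cirrhosis columns = 4 cells. The cells cover virology, blood tests, symptom and adverse-event review and, depending on the group, INR, Fibroscan and ultrasound. Cells with an ECG: 0 of 4.

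**Step 3. Each reading of the end-of-study visit.**

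- *Follow-up week 24 or end of long-term follow-up* (10.3, 13.5.1): no scheduled ECG.
- *Follow-up week 12*, where the schedules place the CD4 count that 10.7.1 attaches to the end of study: no scheduled ECG.
- *SVR4 visit*: an ECG only in subjects selected for an abnormal end-of-treatment ECG, so not a summary of the study population.
- *Last available ECG*: not what the text says. It would also replace the end-of-treatment value by an off-drug SVR4 value in exactly the subjects whose end-of-treatment ECG was abnormal.
- *End of treatment*: the data exist in all subjects, but this is a different visit from the one named, and 10.6 itself uses the end-of-treatment visit as a separate term.

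**Step 4. Data outside the summary.** Unconditional post-baseline ECGs per subject: week 1 and end of treatment = 2. At the target of 600 subjects with full attendance, 2 × 600 = 1,200. If the up to 150 additional people who inject drugs (4.1) are counted on top, 2 × 750 = 1,500. None falls at the visit named in 10.6.

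**Step 5. Distance from treatment.** For follow-up week 24, 13.5.1 states: "The week 24 post-treatment visit (SVR 24) will have a window of -3 days and +28 days". Week 24 is 24 × 7 = 168 days after end of treatment, so the visit falls between 168 − 3 = 165 and 168 + 28 = 196 days off drug. An ECG taken then would say little about on-treatment effects, so adding one at that visit would be the weaker repair.

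**The case against.** The strongest reply is that this is a wording slip that 10.6 itself resolves. The same section states that the ECG is repeated at end of treatment, and a competent analyst would use that recording rather than issue an empty table. The protocol uses end of study loosely elsewhere, and the description in 10.3 concerns what is explained to patients rather than an analysis visit. No ECG parameter is among the safety endpoints in 3.2.2. Visit mapping for a descriptive table is often left to the statistical analysis plan, which is not at hand and may already name end of treatment. All ECGs are collected whichever word is used, so the 1,200 recordings are not lost.

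Much of this stands. A slip is the likely explanation, no data are lost, and the count measures what the summary leaves out rather than what the trial fails to collect. It does not make the sentence right. The protocol did not leave the visit open: it named one, and no post-treatment reading of that name gives an ECG in all subjects. An analysis plan that used end of treatment would depart from the protocol's text, and an analyst should not have to guess which visit was meant.

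**Conclusion.** The point holds. The ECG change summary in 10.6 is set at a visit with no scheduled ECG in either schedule and in none of the four cells of the long-term table. The two post-baseline ECGs planned for every subject stay outside it. This conclusion rests on the protocol alone and on the descriptions of the end of study in 10.3 and 13.5.1; reading the phrase as follow-up week 12 does not change it. The count of 1,200 assumes 600 subjects and full attendance.

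The consequence is limited to a descriptive safety summary. The review and listing of clinically notable ECGs and their recording as adverse events remain in place, and no efficacy result is affected. It should be corrected because the wording is wrong as it stands and the correction is simple.

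**What to change.** Replace the analysis sentence in 10.6 with:

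> *Change from the screening ECG to week 1 and to the end-of-treatment visit (week 12 or week 24, or the visit at premature discontinuation) will be summarised descriptively for every ECG parameter. SVR4 ECGs, taken only after an abnormal end-of-treatment ECG, will be listed separately.*

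The smallest correction would be to change end-of-study to end-of-treatment. Adding week 1 uses the other ECG already planned for everyone, and naming screening as baseline is accurate because it is the only pre-dose ECG scheduled. Keeping the SVR4 ECGs apart prevents selected off-drug values from entering the summary.

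No new ECG, visit or data item is needed. The change goes through the documented amendment process of 19.5.7 and can be carried with the next amendment. The analysis plan should use the same visits before the database lock for the final stage 1 plus stage 2 analysis.

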10.7. Baseline Laboratory Tests

- Complete blood count: white blood cell (WBC), red blood cell (RBC), hemoglobin, hematocrit, platelets, absolute neutrophil, absolute lymphocyte
- Renal function: serum creatinine
- Hepatic Inflammation: Alanine aminotransferase (ALT) and aspartate aminotransferase (AST).
- Hepatobiliary Disease: Bilirubin direct/total, alkaline phosphatase.
- Hepatic Function: Serum albumin
- Glucose (Fasting)
- Coagulation: prothrombin time (PT), International Normalized Ratio (INR).
- Coinfections: Hepatitis B surface antigen, HIV antibody.
- HCV Genotype: Hepatitis C virus exists as one of six distinct genotypes with different clinical characteristics and treatment response rates. Determining HCV genotype does not need to be performed real-time but will be important to establish treatment efficacy across genotypes in particular genotype 1, 3 and 6 which are most prevalent in Thailand and Malaysia.
- Genotype is provisionally determined at screening and confirmed definitively by sequencing of baseline samples. Sequencing will be performed at final analysis on all failures in order to exclude the possibility of reinfection during the study.
- Baseline NS5A Resistance testing is done of all subjects. Results are not expected to be available before treatment initiation.
- Urinalysis.

10.7.1. Additional Laboratory evaluations for HIV co-infected subjects

A documented plasma HIV-1 RNA level must be noted at screening (within 30 days) in those who are anti-HIV positive from a laboratory that has certification. On-study HIV-1 RNA should be performed at a certified laboratory using an approved assay with a lower limit cut-off \leq 50 copies/mL.

Screening and end of study CD4+ cell count may be done by any laboratory that possesses certification (Immunology Quality Assurance (IQA) Program).

10.7.2. Resistance testing for virological failures

NS5A and NS5B resistance testing will be performed for all virological failures. Patients with detectable resistance-associated substitutions (RAS) will be reassessed for RAS 1 year after treatment cessation or at initiation of alternative HCV therapies. These subjects will receive specific counselling and be asked to provide consent for this extended follow-up.

10.8. Fibrosis staging

Following initial evaluation, subjects will be referred for fibrosis staging. Depending on the site organization, staging may be performed on site or at the closest center with the required equipment. Also, based on clinical or biological score results, investigators may decide to refer the subject for hepatologist's advice as cirrhotic subject not only need immediate therapy but also to be scheduled for hepatitis cancer screening and monitoring.

Fibrosis Stage Metavir F1-2-3-4 will be determined by transient elastography (FibroScan^{[66][67][68]}) and secondarily using the APRI score.

Transient elastography, an ultrasound based technique, measures the stiffness of the liver, which is well correlated with the fibrosis stage assessed by liver biopsy. It has been extensively used as a noninvasive method for detection of cirrhosis in patients with chronic liver disease^[69].

In addition, to further characterize patients enrolled in this study, the APRI score will be calculated: the AST to platelets ratio index (APRI score) will be calculated at baseline as it has been shown to predict both significant fibrosis and cirrhosis in patients with chronic hepatitis C^[70].

For therapy, the study population will be stratified according to fibrosis stage i.e. Metavir F4 or < F4 based on the results of transient elastography. After completion of the study, the performances of various fibrosis scores will be evaluated against transient elastography which will be considered as the gold standard. Indeed, one of the study objectives is to assess the potential for scaling up HCV therapy in primary health care settings and such scale-up will have to rely on biological tests readily available such as those used to calculate the APRI or the FIB4 scores or similar scores.

Definition of stage of fibrosis for this study:

Absence of cirrhosis is defined as any one of the following:

- Liver biopsy performed within 24 months of screening of this study showing absence of cirrhosis.
- Fibroscan performed within 12 months of screening or anytime between screening and treatment initiation with a result ≤ 12.5 KPa with M probe or ≤ 10 KPa with XL probe.

Cirrhosis is defined as follows:

- Liver biopsy performed prior to screening of this study showing cirrhosis (Metavir F4 or Modified HAI F6)
- Fibroscan performed within 12 months of screening or anytime between screening and treatment initiation with a result > 12.5 KPa with M probe or > 10 KPa with XL probe.

Fibroscan and APRI score (at screening) are done on all subjects. Fibroscan should be performed within 12 months of screening or anytime between screening and treatment initiation. The final valid Fibroscan result will be used to determine the subject study treatment duration.

A valid fibroscan reading is one done with at least 3 hours fasting and an examination will be considered successful if there were ten valid measurements, and reliable if the interquartile range (IQR)/median for liver stiffness measurement (LSM) was \leq 30%, or the LSM was < 7.1 kPa when the IQR/median for LSM was > 30% (Boursier, Hepatology 2013). The XL probe will be used in patients with unsuccessful or unreliable liver stiffness measurement using the M probe.

The Fibroscan is the reference method for fibrosis assessment. However, in case of failure to get a reliable Fibroscan reading, liver biopsy results or APRI score will be used to diagnose fibrosis. In the

absence of reliable Fibroscan the APRI score will be calculated. An APRI score of > 2 indicates cirrhosis.

10.9. Hair sampling

Hair analysis has proved to be a suitable method to detect chronic or acute abuse of many drugs such as opiates, cocaine, amphetamines and many others.

Additional measures will be taken to pseudonomize the hair analysis data to maintain confidentiality of information about illicit drug use.

Hair samples will be collected at baseline and at end of treatment for all subjects where possible.

These samples will be used to evaluate the effect of drug use on safety and efficacy and to assess drug use in subjects who fail to meet the primary study endpoint (SVR12).

10.10. Quality of life assessment

The PROQOL- HCV quality of life questionnaire is a questionnaire specific to the evaluation of the quality of life in relation with HCV infection. It has been validated in many countries and is translated in different languages.

10.11. Pharmacogenomic assessment

IL28B genotyping is assessed at screening visit only and retrospectively tested from stored plasma to determine its association to treatment response to DAAs.

11. Assessment of efficacy

- Percentage of participants with Sustained Virologic Response at 12 Weeks after end of study drug treatment (SVR12).
 - o Where SVR12 results are missing, SVR24 results, if available, will be used.
 - Where SVR12 results are missing, SVR4 results cannot be used to impute outcome.

Participants will be considered to have achieved SVR12 if HCV RNA is less than the lower limit of quantification (12 IU/mL or 15 IU/mL depending on the laboratory where HCV RNA is done^x) at 12 weeks after the end of treatment.

Categorisation of failures is defined as follows:

- On-Treatment Virologic Failure: HCV RNA ≥ LLOQ at the end of treatment. For example, can
 include patients who experienced virologic breakthrough (confirmed or unconfirmed) or met
 an on-treatment virologic futility rule.
- Virologic Breakthrough: Subcategory of On-Treatment Virologic Failure. Confirmed ≥ 1 log10 IU/mL HCV RNA on-treatment increase from nadir, or confirmed increase in HCV RNA ≥ LLOQ if HCV RNA previously declined to < LLOQ (detected or not detected).

X					
Country	Laboratory	Assay (Machine) used for HCV RNA	Lower limit of quantification	Sites	Visits
Stage 1					
Malaysia	Hospital Kuala Lumpur	Real-Time PCR (COBAS AmpliPrep (CAP) & TaqMan48 (CTM) system)	15 IU/mL	All sites in Malaysia	All visits
Thailand	HIVNAT AIDS Research Centre	Real-Time PCR (Abbott m2000 system)	12 IU/mL	Site 10 (Thailand)	Screening visit only
	Ramathibodi Hospital	Real-Time PCR (Roche COBAS AmpliPrep/COBAS TaqMan system)	15 IU/mL	Site 9 (Thailand)	Screening visit only
	AMS Clinical Service Center	Real-Time PCR (Roche COBAS AmpliPrep/COBAS TaqMan system)	15 IU/mL	Sites 7 & 8 (Thailand)	Screening visit only
	IRD-PHPT Research Group	Real-Time PCR (Abbott m2000 system)	12 IU/mL	All sites in Thailand	All visits except screening visit
Stage 2					
Malaysia	IMR	Real-Time PCR (COBAS 4800 system)	15 IU/mL	All sites in Malaysia	All visits
Thailand	IRD-PHPT Research Group	Real-Time PCR (Abbott m2000 system)	12 IU/mL	All sites in Thailand	All visits

- Virologic Relapse: HCV RNA < LLOQ at end of treatment, but HCV RNA quantifiable (≥ LLOQ) during follow-up; can include patients who experienced late virologic relapse who also achieved primary SVR endpoint.
- Nonvirologic Failure: Did not achieve SVR and did not meet any virologic failure criteria (e.g., adverse event, lost to follow-up).
- Percentage of participants with Sustained Virologic Response at 4 weeks and 24 weeks after end of study drug Treatment (SVR4 and SVR24) will be evaluated in order to provide a comprehensive view of the timecourse of reduction in viral load.
 - Where SVR4 results are missing, SVR12 results, if available, will be used.
 - Where SVR4 and SVR12 results are missing, SVR24 results, if available, will be used.
 - Where SVR24 results are missing, SVR4 or SVR12 results cannot be used to impute outcome.
- Percentage of participants with Alanine Aminotransferase (ALT) normalization normalization (defined as ALT > ULN at baseline and ALT ≤ ULN at a later visit) and of participants with Aspartate Aminotransferase (AST) normalization (defined as AST > ULN at baseline and AST ≤ ULN at a later visit)
- Change from baseline of Quality of life (QoL) measured by PROQOL-HCV questionnaire.
- Change from baseline of HCV NS5A and NS5B sequences in virological failures
 - Sequencing of the HCV non-structural protein 5A (NS5A) and 5B (NS5B) genes will be done retrospectively to identify pre-existing polymorphisms and characterize emerging HCV viral variants.

12. PK assessments

Intensive PK study will beperformed in stage 1 only. Sparse PK samples collection, ARV data and hair samples will be collected in both stages.

